In this study, we use the blood vessels in the skin as a representative vascular bed for examining mechanisms of microvascular dysfunction in humans. Using a minimally invasive technique (intradermal microdialysis for the local delivery of pharmaceutical agents) we examine the blood vessels in a dime-sized area of the skin in healthy young women and men. As a compliment to these measurements, we also draw blood from the subjects and measure circulating factors that may contribute to cardiovascular health.

I.5 *Specify your research question(s), study aims or hypotheses (do not indicate "see protocol")*
The aim of this proposal is to define the mechanistic role of activation of AT2Rs in young men and young women. To accomplish this aim, we will test the following hypotheses:

Hypothesis 1: AT2R activation (C21) will have greater microvascular dilation in young women vs young men.
Hypothesis 2: The dilatory response to C21 will be enhanced in both young women and men with AT1R inhibition (losartan) vs control.

I.6 *Background and significance and/or Preliminary studies related to this project.
(do not indicate "see protocol")*

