needle and then withdraw the needle leaving the tubing in the skin. Any hyperemia related to the insertion subsides in about 60 minutes. When the hyperemia induced by inserting the tubing in the skin subsides, the experiment begins. During this time Lactated Ringer's perfuses the tubing. The researchers tape a fiber optic laser Doppler flowmeter probe and its holder over each microdialysis site. The researchers control the temperature of the holders. The holders start at 33°C (91.4°F). During the experiment, the computerized data acquisition system records heart rate, skin blood flow, and skin temperatures continuously. The researcher and/or an automated critical care monitor measures blood pressure at 5-7 minute intervals.

Local Heating Protocol: The intradermal microdialysis probes are randomly numbered 1 or 2 and assigned to receive doses of Lactated Ringer's (probe 1) or Losartan (probe 2).

Probe 1. Lactated Ringer's only

Probe 2. Lactated Ringer's + Losartan

Initially, Lactated Ringer's flows through all probes. Then the investigational agents are added to the Lactated Ringer's flowing through MD probe 2 for 60 minutes. When the skin blood flow is stable, we perform a 20-minute baseline and set of measurements, including placement of 3 ECG electrodes for the collection of heart rate. After we have collected baseline data, we begin the dose-response protocol. We add identical concentrations of C21 to the perfusate in probes 1 and 2. At 10-minute intervals, we increase the concentration of C21 in the perfusates in identical fashion in probes 1 and 2. The participant receives 10 different concentrations of C21. After perfusing the last concentrations, all MD sites are then warmed to 43°C (108°F) to perform Maximal Skin Blood Flow. At the same time, the researchers switch the fluids at all sites to Ringer's + SNP for about 30 minutes. This causes the blood vessels at the MD sites to dilate or enlarge as much as they can. The researchers then de-instrument the subject, remove the microdialysis fibers, and apply sterile dressings. The subject is given verbal and written instructions for how to care for the microdialysis sites. The researcher measures final vitals before the subject departs.

VII.E.7 *Will you attempt to recontact subjects who are lost to follow-up?*
No - followup is not required in this study

VII.E.9 *Will subjects be provided any compensation for participating in this study?*
Yes

VII.E.10 *Cash*
No

VII.E.11 *Gift Card*
No

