No

XI. Data Analysis

XI.1

Describe the analysis methods you will use, including, if applicable, the variables you will analyze

The primary outcome variable will be cutaneous vascular conductance, which is calculated from laser-Doppler flux/mean arterial pressure. Three-way repeated measures ANOVA (group, MD site, dose) will be used to examine group differences and local microdialysis treatment differences across the doses of pharmacological stimuli. Appropriate post-hoc analyses with corrections for multiple comparisons will be performed when main effects are identified, including potential confounding variables as covariates. Paired t-tests will be used to examine group differences in subject characteristics.

XI.2

Provide the rationale or power analysis to support the number of subjects proposed to complete this study.

Using previously published data that determined differences in cutaneous vascular conductance (CVC), an index of skin blood vessel dilation, the results of a power analysis indicated that 24 young men and women (12 subjects x 2 groups) will be sufficient to detect a meaningful physiological difference (power=0.80, $\alpha=0.05$) of a ~10% change in CVC from baseline between microdialysis treatment sites and sex differences (men and women). Based on the available literature and on prior experience with microdialysis studies, the standard deviation of the difference is ~10%. After accounting for attrition, withdrawals, and screen failures, we conservatively estimate that 44 people will need to be consented and screened in order to arrive at this target number of 24.

XII. Future Research

XII.1

Do you wish to keep any information about subjects involved with this research project so that members of the current research team may contact them in the future for your own research projects?

Yes

XII.2

Do you wish to keep any information about subjects involved with this research project so that [other researchers](#) may contact them for future research?

No

XII.3

List the data or information you will keep:

Name

Race/ethnicity

Birthdate

Sex

Contact information (mailing address, e-mail address, phone number)

XII.4

Does this project involve storing any data, tissues or specimens for future research?

Yes – contribution for future use is optional

XII.5

Describe how you will keep track of those who consent to future use and those who do not and how you will prevent future use for those who do not consent.

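### Section XI.2 claims power 0.80 for both the site contrast and the sex contrast from one standard deviation of the difference; that input fits the site contrast but does not establish 0.80 for the sex contrast (H1)

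*Combined protocol and SAP*

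**What the plan says.** Section I.5 sets two hypotheses. The first, which is also the title question, compares the sexes: "Hypothesis 1: AT2R activation (C21) will have greater microvascular dilation in young women vs young men". The second compares two skin sites: "The dilatory response to C21 will be enhanced in both young women and men with AT1R inhibition (losartan) vs control". Section VII.E.6 places both probes in the same participant, so the second contrast is within subject. It adds that "The participant receives 10 different concentrations of C21".

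Section XI.2 makes one sample size statement: "24 young men and women (12 subjects x 2 groups) will be sufficient to detect a meaningful physiological difference", with power 0.80 and alpha 0.05. The difference is about 10%, described as a "change in CVC from baseline between microdialysis treatment sites and sex differences (men and women"), so one figure covers both contrasts. The variability is given once: "the standard deviation of the difference is ~10" percent. XI.2 states no between-subject SD, no correlation between sites, no sidedness, no test, and no choice of dose or site for the sex comparison.

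Section XI.1 gives the analysis: "Three-way repeated measures ANOVA (group, MD site, dose) will be used to examine group differences" and treatment differences across doses.

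**The concern.** The two contrasts have different error terms. Losartan versus control is a difference within each participant, and its precision depends on the SD of that difference. Women versus men is a difference between independent groups of 12, and its precision depends on how much the compared value varies from person to person. An SD of the difference does not supply that second quantity unless the text says that the same figure applies to both.

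At stake is how a non-significant sex difference would be read. Taken at face value, XI.2 tells the reader that a true 10-point sex difference would be missed 20% of the time. If the between-subject SD is 10 and the test is two-sided, it would be missed about 35% of the time. The text does not let the reader tell which applies.

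**Working it through.** **Inputs from XI.2:** alpha 0.05; difference 10 points; SD 10 points; 12 per sex, 24 in all. Difference and SD are taken to be on the same percentage scale.

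**Assumed, because not stated:** a two-sided test, which matches the non-directional group effect of the ANOVA in XI.1, and one value per subject. One-sided results are shown as well. Power is from the noncentral t distribution.

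**1. Plan's own figure, H2 (paired).** Noncentrality = (10/10) × √n.
- n = 12: √12 = 3.46, 11 df, critical t 2.20; power 0.883.
- n = 24: √24 = 4.90, 23 df, critical t 2.07; power 0.997.
- n = 10 would give 0.803.

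The stated 0.80 is thus met and exceeded for one uncorrected paired contrast.

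**2. Plan's own figure, H1, if 10 is also the between-subject SD.** Noncentrality = (10/10) × √(12/2) = 2.449, with 22 df.

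| Test, 12 vs 12 | Power |
|---|---|
| Two-sided t (critical 2.074) | 0.649 |
| Two-sided, normal approximation | 0.688 |
| One-sided t (critical 1.717) | 0.767 |
| One-sided, normal approximation | 0.789 |

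The two-sided figure does not reproduce 0.80. Two-sided 0.80 at 12 per group needs a standardised difference of 1.197. That is a difference of 1.197 × 10 = 11.97 points at SD 10, or an SD of at most 10/1.197 = 8.36 for 10 points.

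**3. H1, if 10 is only the paired SD.** With equal variances and correlation ρ between the two sites, SD of the difference = SD × √(2(1−ρ)), so the single-site between-subject SD is 10/√(2(1−ρ)). The documents do not give ρ; the values below are assumptions.

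| ρ | Single-site SD | Two-sided power, 12 vs 12 |
|---|---|---|
| 0 | 7.07 | 0.91 |
| 0.3 | 8.45 | 0.79 |
| 0.5 | 10.00 | 0.65 |
| 0.7 | 12.91 | 0.44 |
| 0.8 | 15.81 | 0.32 |

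Power 0.80 is reached at ρ of about 0.28.

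**4. Rounding of the inputs.** With the approximate 10s taken at favourable whole-percent limits (10.49 points, SD 9.5), two-sided power is 0.73. One-sided it is 0.84, but that needs an undeclared one-sided test and both inputs at their limits.

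**5. Precision for H1 at SD 10.** Expected 95% CI half-width = 2.074 × 10 × √(2/12) = 8.47 points.

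**The case against.** The strongest objection is that 0.65 is not the power of the planned test. The ANOVA group effect compares subject means over two sites and up to ten doses. If 10 is the SD of a single measurement, averaging reduces it. Assume a constant 10-point sex difference and an equal correlation r among all 20 measures. The SD of the mean is then 10 × √((1 + 19r)/20), and two-sided power is 0.90 at r = 0.5, 0.80 at r = 0.68, 0.74 at r = 0.8 and 0.69 at r = 0.9. This stands as a limit on the 0.65, which holds for one value per subject with SD 10. It does not support the plan's figure, because XI.2 gives no correlation and does not say that H1 was powered on an average. A constant difference is also unlikely at the lowest doses.

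H1 is worded directionally, and a one-sided normal approximation comes close to the plan at 0.789. However, no one-sided test is declared, the ANOVA group effect is non-directional, and the one-sided t-test itself gives 0.767.

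Finally, VII.B.11 says that a separate written protocol exists, and XI.2 rests on published data that it does not reproduce. Either may contain the missing SD. That is fair, and the point is confined to what XI.2 states.

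A reader might go further and infer that no reading gives 0.80 for H1. Step 3 and the averaging calculation show that some do, under correlations the documents neither give nor exclude. A reader might also infer that H2 falls short once doses are corrected for multiplicity or each sex is tested alone. XI.1 names no correction method and specifies no separate tests by sex, so the documents do not support a figure for that.

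**Conclusion.** The point holds as a gap in support for H1. XI.2 claims 0.80 for a comparison of independent groups and gives no between-subject SD from which it follows. On the most direct use of the stated inputs (SD 10 between subjects, one value per subject, two-sided t-test, 12 per sex), power is 0.65 rather than 0.80. If 10 is only the paired SD, single-site power lies anywhere from 0.91 to 0.32 over assumed between-site correlations of 0 to 0.8, and averaging over sites or doses would change it again.

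It would be too strong to conclude that the trial is underpowered for the sex comparison or must enrol more people. The between-subject SD is unknown, and a value of about 8.4 or less would make the 0.80 correct for a two-sided test. H2 is adequately powered on the stated inputs, for a single uncorrected paired contrast. This should be corrected because H1 is the title question and the repair is small.

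**What to change.** Replace the single power sentence in XI.2 with two.

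- **H2 (paired).** Keep the SD of the difference of 10 and state the power that follows: 0.88 within one sex and above 0.99 with all 24, two-sided, for one uncorrected contrast.
- **H1 (independent groups, 12 per sex).** Name the value compared (dose or doses, site or sites), its between-subject SD and the source, and a two-sided test to match the ANOVA. Then state the resulting power. If that SD is 10 and one value per subject is compared, this is 0.65 for 10 points, or 0.80 for about 12 points.

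If no between-subject SD is available, remove the 0.80 claim for H1, say that its power was not established, and report the sex difference with its 95% CI (expected half-width about 8.5 points at SD 10).

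The cost is one rewritten paragraph and one SD, if the published data behind the power analysis report it. Enrolment does not change, but the stated power for H1 becomes conditional or less favourable.
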